5.2.1.2 Additional Description of Failure Modes

Failure mode counts will be summarized overall, per device, per day and per device per day, as represented in Appendix A by Tables A.5.1, A.5.2, A.6.1 and A.6.2, respectively. A list of the failure modes available in the free form text field describing the “Other” category will be provided. Companion bar plots will be generated for each of these tables.

Note: It is possible that despite a failure having been observed during a 2mL, a draw was attempted at 6mL, such situation would result in failures being counted twice. To avoid this, any failure information with a time stamp ulterior to the time stamp associated with the first failure record will be discarded from the data used to generate the principal tables summarizing the count of failure modes. A separate table will included providing counts of consecutive failures (defined as a failure occurring in a 6mL draw when a failure has already been observed for the immediately preceding 2mL).

5.2.1.3 Additional Description of Failure Remediation

Failure remediation counts, which steps are described in the PIVC rescue decision trees for flush and aspiration procedures represented in Appendix D by Figures D.1.1 and D.1.2, will be summarized for each step overall and per device per day, as represented in Appendix A by Tables A.7.1 and A.7.2, respectively.

5.2.2 Statistical Analysis of Secondary Endpoints

5.2.2.1 Haemolysis

It is hypothesized that:

- The cfHb concentrations observed in blood samples (all vacutainers, at all timepoints) collected from shorter catheters will be greater than that observed in longer catheters.

- The cfHb observed in blood samples (all vacutainers, at all timepoints) collected from catheters with a larger gauge (smaller bore) will be greater than blood collected from smaller gauge (greater bore).
- The cfHb observed in blood samples (all catheters) collected into greater volume vacutainers will be greater than blood collected into smaller volume vacutainers.

Haemolysis will be assessed through:

1. Quantification of average cfHb concentrations measured at each time point listed in red in Table 2.7.1. A linear mixed effect model will be used with cfHb as response and subject as random effect. Time, gauge, length, vacutainer volume and baseline (at D1.2) cfHb (2ml, 6ml measures will be used as separate continuous variables and will be retained in the model if significant) will be fixed effects. An example of the summary statistics table and associated graphical representation are provided in Appendix A by Table A.10.2 and in Appendix B by Figure B.3.1, respectively.
2. Rate of occurrence measured using the results of the cfHb concentrations at each time point listed in red in Table 2.7.1. Samples will be considered positive for haemolysis for cfHb concentration $\geq 50\text{mg/dL}$ ¹. A logistic mixed effect model will be used with haemolysis occurrence as response and subject as random effect. Time, gauge, length, vacutainer volume and baseline (at D1.2) cfHb will be fixed effects. Tables summarizing occurrence rates per device per time point and associated graphical representation will be similar to the one provided for rate of occurrence measured using the results of the AU480 analysis (see next item) in Appendix A by Table A.10.2 and in Appendix B by Figures B.4.1 and B.4.2, respectively. Contrast based multiple comparisons will be used to compare haemolysis rate between conditions (between gauge, between length) at each timepoint.
3. Rate of occurrence measured using the results of the AU480 Analysis at each time point listed in red in Table 2.7.1. Samples will be considered positive for haemolysis for AU480 output of + (50-99mg/dL), ++ (100-199mg/dL), +++ (200-299mg/dL), ++++ (300-500mg/dL) and +++++ (>500mg/dL), i.e. anything different from N (<50mg/dL)². A logistic mixed effect model will be used with haemolysis occurrence as response and subject as random effect. Time, gauge, length, vacutainer volume and baseline (at D1.2) cfHb will be fixed effects. Examples of the table summarizing occurrence rates per device per time point and associated graphical representation are provided in Appendix A by Table A.10.2 and in Appendix B by Figures B.4.1 and B.4.2, respectively. Contrast based multiple comparisons will be used to compare haemolysis rate between conditions (between gauge, between length) at each timepoint.
4. Rate of occurrence measured using the results of the visual assessment at each time point listed in red in Table 2.7.1. Samples will be considered positive for haemolysis for visual values $\geq 50\text{mg/dL}$, as shown on the reference chart. A logistic mixed effect model will be used with visually observed haemolysis occurrence as response and subject as random effect. Time, gauge, length, Vacutainer tube volume and baseline (at D1.2) cfHb will be fixed effects. An example of the table summarizing occurrence rates per device per time point is provided in Appendix A by Table A.10.2. Graphical representation will be similar to the ones given as example for the AU480 analysis. Contrast based multiple comparisons will be used to compare haemolysis rate between conditions (between gauge, between length) at each timepoint.

In each case, i.e. for cfHb, AU480 and visual assessment, modeling will be preceded by an assessment of the importance of potential covariates using the Boruta algorithm. The covariates of interest will include,

¹A separate assessment of the relationship between the cfHb and AU480 measurements will be performed in order to check the validity of this threshold, which could be modified upon review of these results.

²A separate assessment of the relationship between the cfHb and AU480 measurements will be performed in order to check the validity of this threshold, which could be modified upon review of these results.

but will not be limited to:

- Presence of thrombus
- Size of thrombus
- Proximity of thrombus to tip of catheter
- Draw rate
- Screening Blood Testing (as provided by Blood Testing CRF)
 - Coagulation Panel: PT & aPTT
 - Platelet Aggregometry: ADP, TRAP & Collagen Induced Maximal Amplitude
 - Blood Screening: Blood Glucose & Triglycerides
 - Liver Panel: ALT Average Measurement & AST Average Measurement

The significance of the most important features will be assessed by inclusion in the corresponding models and only significant covariates will be retained in the final model.

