5.2.2.2 Blood draw fill time

It is hypothesized that:

- The blood draw duration observed for blood samples (all vacutainers, at all timepoints) collected from shorter catheters will be decreased when compared to longer catheters of the same gauge.
- The blood draw duration observed for blood samples (all vacutainers, at all timepoints) collected from smaller gauge (larger bore) catheters will be decreased when compared to larger gauge (smaller bore) catheters of the same length, over time.
- The blood draw duration observed for blood samples (all catheters, at all timepoints) collected into greater volume vacutainers will be increased when compared to smaller volume vacutainers.

A linear mixed effect model will be used with blood draw fill time as response and subject as random effect. Time, device configuration (gauge, length and their interaction), Vacutainer tube volume and baseline (at D1.2) blood draw fill time will be fixed effects. Contrast based multiple comparisons will be used to compare blood draw fill time between conditions (between gauge, between length) at each timepoint. Example tables for summary statistics (overall and per time point for each Vacutainer tube volume are given in the Appendix section by Table A.9.1 and Table A.9.2, respectively. Graphical representations of distribution of blood draw time per device is provided in Figure B.5.1 and of average blood draw time is shown in the Appendix section by Figure B.5.3. Example tables for ANOVA tables (Table A.9.3) and multiple comparisons (Table A.9.4) can be found in the Appendix A

5.2.2.3 Relationship between catheter blood draw patency indwell time and presence of intra/extravenous thrombi, thrombus length, thrombus type catheter angle/tip location *in situ*, catheter length in vessel, vein depth from skin surface, C/V ratio, and vessel anatomy

Relationship, if any, will be assessed through the computation of:

1. Summary statistics stratified by indwell time considered as a discrete variable (0, 6, 24, 30, 48, 54, 72 hours)
2. Scatter plot showing time between initial Thrombus observation to time of removal per Device Configuration
3. Bar plot showing percentage of thrombus for each time point per device configuration
4. Scatter plot showing thrombus length as a function of time grouped by device configuration
5. Relationship between flush technique and presence of Thrombus

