6. Summary statistics and boxplot showing time between time of initial thrombus observation and device removal per device configuration

7. Importance of covariates will be computed with Boruta algorithm with a survival random forest model (an example output from the algorithm is provided in the Appendix by Figure B.7.1).
8. Test of predictive performance for the most important features (confirmed by the Boruta algorithm) using a leave-one-out strategy

In addition to the variables used in the primary endpoint survival model (device gauge and length), investigated baseline characteristics will be:

- Venous thrombosis
- Thrombus Length
- Thrombus Type
- Angles of insertion (Acute Inferior and Superior)
- Catheter to vein (C/V) ratio
- Catheter length in vessel
- Presence of side branches and/or intravenous valves
- Age
- Gender
- Height
- Weight
- BMI
- Dominant arm
- Medical history questionnaire responses
- Exploratory endpoints:
 - Vein collapse
 - Phlebitis
 - Dislodgement
 - Extravasation
- item Screening Blood Testing (as provided by Blood Testing CRF)
 - Coagulation Panel: PT & aPTT
 - Platelet Aggregometry: ADP, TRAP & Collagen Induced Maximal Amplitude
 - Blood Screening: Blood Glucose & Triglycerides
 - Liver Panel: ALT Average Measurement & AST Average Measurement

The Boruta algorithm does not require specific formatting and generally works well with continuous and categorical variables. In some cases, it might be interesting to move from continuous format to a categorical one (e.g. age) depending on the final analysis. Categorization rules will be detailed whenever performed.

5.2.2.4 Evaluation of changes in vessel dimensions, PIVC position (insertion angle and *in situ* tip position), and haemodynamics from baseline throughout indwell time

These will be evaluated using:

- C/V ratio
- Catheter Length in Vessel (mm)
- Catheter Insertion Angle - acute inferior border angle (deg)
- Catheter Insertion Angle - acute superior border angle (deg)
- Blood Draw Time (sec)
- Blood Flow Velocity (cm/sec)
- *In situ* tip position (Mid-Stream & Wall Contact)

For each of these characteristics, summary statistics by indwell time considered as a discrete variable (0, 6, 24, 30, 48, 54, 72 hours) and line and bar plots will be generated on average for continuous and by proportion for categorical responses, respectively.

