Line plots will be similar to the example provided for cfHb in Figure B.3.2 and bar plots will be similar to the example provided for Haemolysis occurrence in Figure B.4.1, both represented in Appendix B.

Mixed effect models will be used with corresponding response and subject as random effect. Time, gauge, length, Vacutainer tube volume and baseline measurement of response will be fixed effects. Depending on the type of the response variable, the models will be:

- Linear: C/V ratio, catheter length, catheter insertion angles and blood flow velocity
- Logistic: Tip positions

Depending on model results, contrast based multiple comparisons will be used to compare means between conditions (between gauge, between length) at each timepoint. Results will be provided in Tables similar to the example given for Blood Draw Fill time in Tables A.9.3 and A.9.4, as can be found in the Appendix A.

The relationship between C/V ratio and Blood Draw Time as well as between C/V ratio and Blood Flow Velocity will be investigate using relevant graphical representation (scatter plots) and measure of association.

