Time Point (hours)	Characteristic	BD Nexiva (22G x 1 inch)	BD Nexiva (22G x 1.75 inch)	BD Nexiva (20G x 1 inch)	BD Nexiva (20G x 1.75 inch)	Overall
0	Thrombus (Yes/No)					
	Yes	14 (70.0%)	13 (65.0%)	16 (80.0%)	10 (50.0%)	53 (66.2%)
	No	6 (30.0%)	7 (35.0%)	4 (20.0%)	10 (50.0%)	27 (33.8%)
	Total	20	20	20	20	80
6	Thrombus (Yes/No)					
	Yes	14 (70.0%)	12 (63.2%)	16 (80.0%)	10 (50.0%)	52 (65.8%)
	No	6 (30.0%)	7 (36.8%)	4 (20.0%)	10 (50.0%)	27 (34.2%)
	Total	20	19	20	20	79
24	Thrombus (Yes/No)					
	Yes	12 (66.7%)	11 (61.1%)	16 (80.0%)	10 (50.0%)	49 (64.5%)
	No	6 (33.3%)	7 (38.9%)	4 (20.0%)	10 (50.0%)	27 (35.5%)
	Total	18	18	20	20	76
30	Thrombus (Yes/No)					
	Yes	10 (62.5%)	11 (64.7%)	15 (78.9%)	10 (50.0%)	46 (63.9%)
	No	6 (37.5%)	6 (35.3%)	4 (21.1%)	10 (50.0%)	26 (36.1%)
	Total	16	17	19	20	72
48	Thrombus (Yes/No)					
	Yes	6 (54.5%)	10 (62.5%)	15 (83.3%)	10 (50.0%)	41 (63.1%)
	No	5 (45.5%)	6 (37.5%)	3 (16.7%)	10 (50.0%)	24 (36.9%)
	Total	11	16	18	20	65
54	Thrombus (Yes/No)					
	Yes	3 (42.9%)	8 (57.1%)	13 (81.2%)	10 (50.0%)	34 (59.6%)
	No	4 (57.1%)	6 (42.9%)	3 (18.8%)	10 (50.0%)	23 (40.4%)
	Total	7	14	16	20	57
72	Thrombus (Yes/No)					
	Yes	3 (50.0%)	7 (58.3%)	8 (72.7%)	8 (44.4%)	26 (55.3%)
	No	3 (50.0%)	5 (41.7%)	3 (27.3%)	10 (55.6%)	21 (44.7%)
	Total	6	12	11	18	47

B Figures

[figure not shown]
B.1 Survival

Figure B.1.1: Survival Curve for Indwell Time per Device Configuration. Color bands represent 95% Confidence Intervals

B.2 Indwell Time

Figure B.2.1: Boxplot for Indwell Time per Device Configuration

B.3 Blood Analysis

B.3.1 cfHb

Figure B.3.1: Boxplot for cfHb per Device Configuration for each Timepoint

[figure not shown]
[figure not shown]

Figure B.3.2: Lineplot for cfHb per subject and Device Configuration over time

B.4 Haemolysis Occurrence

Figure B.4.1: Barplot for Haemolysis Occurrence (assessed with AU480) per Device Configuration

[figure not shown]
[figure not shown]

Figure B.4.2: Barplot for Haemolysis Occurrence (AU480 measurements) per Device Configuration for each Timepoint

B.5 Blood Draw Fill Time

Figure B.5.1: Boxplot for Blood Draw Fill Time per Device Configuration

[figure not shown]

Figure B.5.2: Estimated Blood Draw Fill Time Difference (with 95% CI) between Device Configurations for 2 and 6mL Vacutainer tubes

[figure not shown]

Figure B.5.3: Lineplot for Blood Draw Fill Time per Device Configuration at each captured timepoint

[figure not shown]
[figure not shown]

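### The secondary mixed models have no catheter-level random effect, so length effects pooled over timepoints get standard errors that are too small whenever a participant's two catheters differ beyond length

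*SAP*

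**What the plan says.** Under SAP 2.3.1 a participant receives one length in one arm and the other length, in the same gauge, in the other arm. Length therefore varies between catheters within a person, and gauge varies between persons. Table 2.7.1 gives seven draws per catheter, each into a 2 mL and a 6 mL tube, and two ultrasound scans at each of the seven post-insertion windows.

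The secondary models are specified as follows:

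- cfHb concentration (5.2.2.1, item 1): "A linear mixed effect model will be used with cfHb as response and subject as random effect".
- Haemolysis occurrence (5.2.2.1, items 2 and 3, with item 4 worded alike): "A logistic mixed effect model will be used with haemolysis occurrence as response and subject as random effect".
- Fill time (5.2.2.2): "A linear mixed effect model will be used with blood draw fill time as response and subject as random effect".
- Vessel, position and flow measures (5.2.2.4): "Mixed effect models will be used with corresponding response and subject as random effect".

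No catheter or arm term, random length slope, within-catheter covariance or robust variance is named. Protocol 10.6 names linear mixed-effects models without giving random effects.

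On pooling over time, the SAP points both ways. The fill-time length hypothesis concerns "The blood draw duration observed for blood samples (all vacutainers, at all timepoints) collected from shorter catheters", and the cfHb hypothesis is framed likewise. Item 1 names no per-timepoint contrast. SAP 5.2.4 removes non-significant interactions. The caption of Figure B.5.2 reads "Estimated Blood Draw Fill Time Difference (with 95% CI) between Device Configurations for 2 and 6mL Vacutainer tubes", with Figure B.5.4 as the separate version by timepoint. Against that, items 2-4 and 5.2.2.2 plan contrasts at each timepoint, and mock Tables A.9.3 and A.9.4 keep non-significant interactions and report by tube and timepoint.

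For 5.2.2.4 the fixed effects are given as: "Time, gauge, length, Vacutainer tube volume and baseline measurement of response will be fixed effects".

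**The concern.** The two catheters of one person sit in different arms, each with its own vein, tip position and thrombus status. SAP 5.2.2.3 lists such features as possible influences on indwell time, and Protocol 2.1 says that tip position, insertion angle and the catheter-to-vein (C/V) ratio may affect haemolysis. Some variation between catheters beyond length is therefore plausible. A participant intercept cannot carry it, and the cfHb baseline is one venipuncture session per participant, so that cannot carry it either. The variation goes into the residual and is averaged down over as many as 14 values per catheter, although each participant supplies only one catheter of each length.

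Length is the factor the design pairs within participants (Protocol 4.2). Confidence intervals for long versus short would be too narrow, and p < 0.05 would occur too often, for cfHb, haemolysis rate, fill time and the ultrasound measures. The same p-values also decide which terms stay in the model under 5.2.4. SAP 5.2 gives estimation and significance similar importance, and SAP 2.6 sends haemolysis items 1 and 2 into a preliminary analysis for business decisions.

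**Working it through.** **The plan's own figure.** The documents give no standard error or power for these models. Their only power figure, 0.8054 in SAP 2.4, belongs to the primary log-rank test. It reproduces: expected events are 19 × 0.875 + 20 × 0.5 = 26.6, and the Lakatos method gives 0.806. This point does not change it.

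**Inputs.** There are 40 participants with 2 catheters each (SAP 2.1, 2.3.1), 7 draws × 2 tubes = 14 values per catheter (Table 2.7.1), and a 5% level (5.2.4), taken as two-sided. rho is assumed at 0.05, 0.10 and 0.20.

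Attrition uses exponential failure at the medians of 1 and 3 days in SAP 2.4. Expected values per catheter are 2 × Σ 0.5^(t/median) over t = 0, 6, 24, 30, 48, 54, 72 h. This gives 6.7 (median 24 h) and 10.4 (median 72 h), mean 8.6.

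**Formula.** With n values per catheter, of which m enter the contrast, and allowing for the participant intercept absorbing about half the catheter variance:

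true SE / reported SE = √{[(1 − rho) + m·rho] / [(1 − rho) + rho·n/(2n − 1)]}

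actual type I error = 2Φ(−1.96 / ratio)

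Example with m = n = 14 and rho = 0.10: numerator 0.9 + 1.4 = 2.3; denominator 0.9 + 0.1 × 14/27 = 0.952; ratio √2.416 = 1.55; type I error 2Φ(−1.26) = 20.7%.

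**Check by exact balanced-design variances** (catheter plus residual variance = 1, rho = 0.10). The true SE is √[2(0.1 + 0.9/14)/40] = 0.091. The within-participant mean square is [39 × 2.3 + 1040 × 0.9]/1079 = 0.951, so the participant-only model reports √[2 × 0.951/(14 × 40)] = 0.058. The ratio is again about 1.56.

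**Linear models.** The simulations used 2,000 data sets per setting, REML, no length effect and an assumed participant intraclass correlation of 0.3. Cells show type I error, with the SE ratio first in the formula rows.

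| Length contrast | rho 0.05 | rho 0.10 | rho 0.20 |
|---|---|---|---|
| Times and tubes pooled, complete: formula | 1.30, 13.2% | 1.55, 20.7% | 2.00, 32.6% |
| same, simulated | 13.8% | 19.6% | 32.1% |
| Times and tubes pooled, attrition: formula (m = n = 8.6) | 1.19, 9.9% | 1.36, 14.9% | 1.67, 24.0% |
| same, simulated | 10.1% | 16.5% | 22.2% |
| One tube, times pooled (Figure B.5.2 format), complete: formula (m = 7) | 1.15, 8.9% | 1.30, 13.1% | 1.56, 20.9% |
| same, simulated, complete | 8.3% | 13.3% | 18.9% |
| same, simulated, attrition | 6.4% | 9.8% | 13.6% |
| One timepoint, both tubes: formula (m = 2) | 1.04, 5.9% | 1.08, 6.8% | 1.15, 8.9% |
| One timepoint, one tube (Table A.9.4 format): formula (m = 1) | 1.01, 5.3% | 1.03, 5.6% | 1.05, 6.2% |

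At rho = 0 the pooled test rejects in 4.7% (complete) and 4.9% (attrition) of data sets. With a catheter intercept added, it rejects in 3.7-6.1% over rho 0 to 0.20. Gauge tests stay at 5-7% under either model.

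**Logistic models** (times and tubes pooled, participant variance 1 on the logit scale assumed). At the 13.9% and 25.5% rates that Protocol 2.1 cites from emergency patients, type I error is 9.8%, 14.2% and 23.4% with complete data and 8.1%, 11.5% and 16.7% with attrition. At the 3.3% rate cited for routine samples it is 5.4%, 7.8% and 12.2%, and 5.2%, 6.6% and 8.0%.

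**5.2.2.4 wording.** The models listed there (C/V ratio, catheter length, insertion angles, flow velocity, tip position) have no tube, so a tube-volume effect has no meaning. It was probably carried over, since blood draw time is in that section's response list. SAP 6.3 places baseline sonography before insertion, and Table 2.7.1 marks D1.1 as having no catheter in place, yet Table A.3.1 shows a baseline tip position. A baseline for tip position, insertion angle and catheter length is therefore undefined.

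**The case against.** The best defence is that pooling is partly inferred. The hypotheses can be read as claims about every timepoint separately, the one mock model output keeps its interactions, and Figure B.5.2 is known here only by a caption that 5.2.2.2 does not cite. In the Table A.9.4 format the error is negligible. That stands as a limit on scope. But 5.2.4 directs that non-significant interactions be dropped, and once length-by-time is gone, the contrast at each timepoint is the pooled one. cfHb item 1 has no per-timepoint contrast at all.

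Second, SAP 5.2.4 plans Tukey or Sidak adjustment where appropriate. With six device contrasts the Sidak level is 1 − 0.95^(1/6) = 0.85% each. At the simulated ratios for the Figure B.5.2 format (1.16, 1.28, 1.52), the actual per-contrast rates are about 2.3%, 4.0% and 8.3%. The absolute rates above thus do not describe adjusted contrasts. The SE ratio is unchanged, however, and an unadjusted main effect gets no relief.

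Third, covariates may absorb some catheter variance: thrombus and draw rate in the haemolysis models, and an arm-specific pre-insertion scan for C/V ratio and flow. rho is defined after covariates, so this lowers rho but does not guarantee zero. The residual-plot review in 5.2.4 names no check for clustering by catheter.

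Fourth, for catheter length in vessel a null of no difference between 1 and 1.75 inch devices is not credible, so only interval width matters there. This is correct.

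Finally, rho is unknown, and this is a feasibility study without acceptance criteria. Both are true, and they bear on size and rank, not on whether the specification is wrong.

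**Conclusion.** The specification is wrong for length effects pooled over timepoints and should be corrected. Given any positive catheter variance, the direction is certain. The size depends on rho, which the documents do not give. For rho from 0.05 to 0.20, true SEs in the linear models are about 1.2 to 2.0 times those reported when times and tubes are pooled, and smaller for one tube. The logistic models err in the same direction by amounts that depend on the event rate, and at low rates with attrition the error is slight.

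The ultrasound models have the same number of observations per catheter (2 scans × 7 windows). rho could be larger there because the same catheter is re-measured. At an assumed 0.5 the pooled type I error would be 44-52%, but no figure in the documents supports that value.

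There is no effect on the primary endpoint. The tube-volume and baseline points in 5.2.2.4 hold but are minor.

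**What to change.** Add a random intercept for catheter (arm) nested in participant to every mixed model in SAP 5.2.2, and state the full random-effects structure. Where that variance is estimated at zero, keep the participant-only fit.

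In 5.2.2.4, remove tube volume from the models for C/V ratio, catheter length, insertion angles, flow velocity and tip position. Drop the pre-insertion baseline term for tip position, insertion angle and catheter length. If the first post-insertion scan (D1.3) is used, confine it to describing change over time. It should not be an adjustment in the length comparison, because catheter length can itself affect it.

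The cost is one model term and two wording corrections, with no new data. If catheters truly do not differ, the pooled length SE grows by about 4% (simulated mean 0.0521 against 0.0500 with complete data) and the test becomes slightly conservative, at about 4%. Otherwise intervals for length widen, as they should. Convergence warnings are possible in the sparse logistic models.
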